390 angiography. The statistical analysis plan will be detailed in a separate document.

391 **8.0 General Principles for Analysis**

392 **8.1 Analysis Cohort**

393 Unless otherwise stated, all treatment comparison analyses will follow the intention-to-treat
394 principle with all randomized eyes included and each eye analyzed according to the randomized
395 treatment assignment, regardless of treatment actually received.

396 **8.2 Visit Windows for Analysis**

397 For common visits, the analysis windows will be defined according to Table 3. For visits falling
398 in more than 1 window, priority will be given to the key outcome visits. Otherwise, the visit will
399 be assigned to the earlier window (e.g., a visit on day 42 would be assigned as the 1-month visit).

400 **Table 3. Analysis Windows for Outcome Visits**

| Visit (Protocol Window) | Target | Analysis Window | |
|---|---------------------------------|-----------------|-----------------|
| 1 Month (± 1 week) | 4 weeks | 14 – 42 days | (2 – 6 weeks) |
| 2 Month (± 1 week) | 8 weeks | 42 – 70 days | (6 – 10 weeks) |
| 3 Month (± 1 week) | 12 weeks | 70 – 98 days | (10 – 14 weeks) |
| 4 Month/Primary Outcome * (± 2 week) | 16 weeks | 84 – 224 days | (12 – 32 weeks) |
| ~6 Month/2-Month Post Outcome (± 2 week) | 8 weeks after 4-Month visit | 140 – 280 days | (20 – 40 weeks) |
| ~8 Month/4-Month Post Outcome* (± 2 week) | 16 weeks after 4-Month visit | 168 – 336 days | (24 – 48 weeks) |

401 *Key visits

402 **8.3 Missing Data**

403 The strategy for handling missing data generally is included with the description of each
404 individual analysis. Where not otherwise specified, only participants with non-missing data are
405 included in the analysis.

406 **8.4 Outliers**

407 To help ensure that statistical outliers do not have undue impact on analyses of continuous
408 outcomes including visual acuity, OCT central subfield thickness (primary outcome) and retinal
409 volume, change in continuous outcomes will be truncated to ± 3 standard deviations based on the
410 overall mean and standard deviation at the primary outcome visit for primary outcome
411 completers' data, irrespective of treatment group. Visual acuity letter score, change in visual
412 acuity from baseline, OCT central subfield thickness, change in CST from baseline, and change
413 in retinal volume from baseline will be truncated. Truncation will be performed after imputation
414 of missing data and LOCF where applicable (i.e., raw data will be used for imputation).

415 **8.5 Model Assumptions**

416 All model assumptions, including linearity, normality of residuals, and heteroscedasticity, will be
417 verified. If model assumptions are not reasonably satisfied, then covariates may be categorized
418 or excluded, and a nonparametric approach, robust estimation method, or transformation may be
419 considered.

420 **8.6 Type I Error Rate**

421 There is no formal adjustment for multiplicity to compensate for the number of outcomes being
422 compared. All comparisons are conducted at alpha level 0.05 unless otherwise noted. In
423 particular, a number of sensitivity analyses and a non-ITT analysis are proposed along with the
424 primary analysis. The intent of these analyses is to explore the effect of primary analysis
425 assumptions on study conclusions, and if they are different, explain why. These analyses are not
426 a substitute for the primary analysis, and primary conclusion will be based on the pre-specified
427 primary analysis. Only 3 of the secondary outcomes of “primary interest” will be compared

428 statistically. Two of these, change in central subfield volume and percentage of participants
429 below the threshold for DME on OCT, are expected to be correlated with the primary outcome,
430 and are intended to help support and interpret the primary outcome findings and interpretation,
431 not to form the basis for independent conclusions.

432

433 **References**

434 Baker CW, Glassman AR, Beaulieu WT, et al. Effect of Initial Management With Aflibercept vs
435 Laser Photocoagulation vs Observation on Vision Loss Among Patients With Diabetic Macular
436 Edema Involving the Center of the Macula and Good Visual Acuity: A Randomized Clinical
437 Trial. *JAMA*. Published online April 29, 2019. doi:10.1001/jama.2019.5790

438 Benjamini Y, Hochberg Y. Controlling the False Discovery Rate: A Practical and Powerful
439 Approach to Multiple Testing. *Journal of the Royal Statistical Society Series B*
(Methodological). 1995;57(1):289-300.

441 Localio AR, Margolis DJ, Berlin JA. Relative risks and confidence intervals were easily
442 computed indirectly from multivariable logistic regression. *J Clin Epidemiol*. 2007;60(9):874-
443 882.

444 Sullivan TR, White IR, Salter AB, Ryan P, Lee KJ. Should multiple imputation be the method of

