333 prior to randomization or plans to do so in the next 4 months.

334 8. Participation in an investigational trial that involved treatment within 30 days of randomization
335 with any drug/device that has not received regulatory approval for the indication being studied.

336 • *Note: study participants cannot participate in another investigational trial that involves
337 treatment with an investigational drug or device while participating in the study.*

338 9. Blood pressure > 180/110 (systolic above 180 or diastolic above 110).

339 • *If blood pressure is brought below 180/110 by anti-hypertensive treatment, individual can
340 become eligible.*

341 10. Systemic anti-VEGF or pro-VEGF treatment within 4 months prior to randomization.

342 • *These drugs should not be used during the study.*

343 11. For women of child-bearing potential: pregnant or intending to become pregnant within the
344 next 8 months.

345 • *Women who are potential study participants should be questioned about the potential for
346 pregnancy. Investigator judgment is used to determine when a pregnancy test is needed.*

347 12. Individual is expecting to move out of the area during the 8 months of the study.

348 **2.2.2 Study Eye Criteria**

349 To be eligible, the study participant must have at least one eye meeting all of the inclusion criteria
350 and none of the exclusion criteria listed below.

351 A participant can have only one study eye. If a participant has two eligible eyes, the eye with the
352 greatest central subfield will be selected as the study eye and the non-study eye will be followed
353 to evaluate any potential contralateral effect.

356 The eligibility criteria for a study eye are as follows:

357 Inclusion

358 a. Best corrected E-ETDRS visual acuity letter score ≥ 79 (i.e., 20/25 or better)

359 b. Ophthalmoscopic evidence of central-involved DME, confirmed by CST on spectral domain
360 OCT:

361 ■ Zeiss Cirrus: $\geq 290\mu\text{m}$ in women, and $\geq 305\mu\text{m}$ in men
362 ■ Heidelberg Spectralis: $\geq 305\mu\text{m}$ in women, and $\geq 320\mu\text{m}$ in men
363 c. Media clarity, pupillary dilation, and study participant cooperation sufficient for adequate
364 OCT.

365

366 Exclusion

367 d. Macular edema is considered to be due to a cause other than DME.
368 • *An eye should not be considered eligible if: (1) the macular edema is considered to be
369 related to ocular surgery such as cataract extraction or (2) clinical exam and/or

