370 investigator assessment of OCT suggests that vitreoretinal interface abnormalities (e.g., a
371 taut posterior hyaloid or epiretinal membrane) are contributing to the macular edema.*
372 e. An ocular condition is present such that, in the opinion of the investigator, any visual acuity
373 loss would not improve from resolution of macular edema (e.g., foveal atrophy, pigment
374 abnormalities, dense subfoveal hard exudates, nonretinal condition).
375 f. An ocular condition is present (other than DME) that, in the opinion of the investigator, might
376 affect visual acuity during the course of the study or require intraocular treatment (e.g., vein
377 occlusion, uveitis or other ocular inflammatory disease, neovascular glaucoma, etc.)
378 g. Cataract is present that, in the opinion of the investigator, may alter visual acuity during the
379 course of the study.
380 h. History of major ocular surgery (including cataract, scleral buckle, any intraocular surgery,
381 etc.) within prior 4 months or major ocular surgery anticipated during the study period.
382 i. Any history of prior laser or other surgical, intravitreal, or peribulbar treatment for DME or
383 DR (such as PRP, focal/grid macular photocoagulation, intravitreal or peribulbar
384 corticosteroids, or anti-VEGF) within the prior 12 months.
385 • *If treatment was given more than 12 months prior, no more than 4 prior intraocular
386 injections*
387 • *Enrollment will be limited to a maximum of 15% of the planned sample size with any
388 history of anti-VEGF treatment and a maximum of 15% with any history of PRP.*
389 j. Anticipated need to treat DME or DR during the study period (Note: any DME treatment
390 during the study must follow criteria in section 3.6).
391 k. History of topical steroid or NSAID treatment within 30 days prior to randomization.
392 l. History of YAG capsulotomy performed within 2 months prior to randomization
393 m. Any history of vitrectomy.
394 n. Aphakia
395 o. Uncontrolled glaucoma

396 **2.2.3 Non-Study Eye**

397 Subjects can have only one study eye. There are no eligibility or exclusion criteria with respect to
398 the non-study eye.

399

400 **2.3 Screening Evaluation**

401 **2.3.1 Historical Information**

402 After informed consent has been signed, a potential participant will be evaluated for study
403 eligibility through the elicitation of a medical history and performance of an ocular examination
404 by study personnel to screen for exclusionary conditions.

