548 completed within the time window of a visit. If data from a testing procedure is unusable (ex. if
549 OCT is ungradable), the participant may be asked to repeat the procedure during an additional
550 visit, whether part of usual care or solely to repeat the procedure.

551 **3.4 Early Termination Visit**

552 Study participants who request to withdraw will be asked to have a final closeout visit at which
553 the testing described for study visits will be performed.

554 **3.5 Unscheduled Visits**

555 Additional visits may occur as required for usual care of the study participant. Testing procedures
556 at unscheduled visits are at investigator discretion. However, it is recommended that procedures
557 that are performed should follow the standard DRCR Retina Network protocol for each procedure.

558 **3.5.1 DME Treatment Initiation Visit**

559 Participants for whom alternative treatment for DME is planned for the first time at an unscheduled
560 visit (e.g. anti-VEGF or corticosteroid intravitreous injection, PRP, focal/grid laser, or vitrectomy)
561 will be asked to complete the study procedures above before the treatment is administered. Usual
562 care vision (e.g. Snellen charts) will be acceptable if the eye is already dilated when treatment is
563 planned.

564 **3.6 Alternative Treatment for CI-DME**

565 Treatment for CI-DME must not be given unless one of the following criteria have been met or
566 protocol chair approval is obtained:

- 567 ○ 1) at least 10 letter decrease in visual acuity from baseline presumed to be from
568 DME at a single visit or
- 569 ○ 2) 5 to 9 letter decrease in visual acuity from baseline presumed to be from DME
570 at two-consecutive visits at least 21 days apart.

571 Once criteria are met, alternative treatment is at the discretion of the investigator as part of usual
572 care. If alternative treatment is given, study device use will be discontinued and participation in
573 the study will be discontinued following the 4-month/primary outcome visit (or next study visit, if
574 after 4 months).

575 **3.7 Participant Access to Study Device at Study Closure**

576 The study device is not commercially available and must be returned at the end of the study.
577 Participants who withdraw from the study (or do not return for the final visit within the allowable
578 window) will be asked to return the device as soon as possible.

579

CHAPTER 4: STUDY DEVICES

580 **4.1 Description of the Investigational Device**

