833 A test of superiority will be used in evaluating the following hypotheses for the primary outcome:

834 Null Hypothesis (H_0): There is no difference in the mean change in CST from baseline to 4 months
835 between photobiomodulation (PBM) and sham groups.

836 Alternative Hypothesis (H_a): There is a difference in the mean change in CST from baseline to 4
837 months between PBM and sham groups.

838 Similar hypothesis tests will be conducted for all secondary, exploratory, and safety outcomes.

839 **7.3 Sample Size**

840 **7.3.1 Outcome Projections:**

841 To estimate the standard deviation (SD) of change in OCT CST, data from the DRCR Retina
842 Network Protocol A (Treatment for Central-Involved Diabetic Macular Edema in Eyes with Very
843 Good Visual Acuity) was used. The Protocol A cohort of eyes with 20/25 baseline visual acuity
844 and central subfield thickening treated with modified-ETDRS laser was used for the estimation.
845 In protocol A, 42 eyes in the modified-ETDRS laser group completed a visit within 4 months of
846 randomization. The SD of change in CST adjusted for baseline CST in these eyes was 50 microns
847 (personal communication, [name]). The mean change in CST was -2 microns.

848 The expected change and standard deviation of CST in an untreated group is unknown at this time.

849 **7.3.2 Sample Size Estimates**

850 Table 1 shows total sample size estimates under several scenarios. These calculations assume a
851 Type I error rate of 5%, 90% power, and a two-sided test of superiority (see Section 7.6) with a
852 null hypothesis of no difference between the groups (see Section 7.2).

853

854 **Table 1: Total Sample Size Under Various Assumptions for True Mean Change and**
 855 **Standard Deviation**

Mean Treatment Group Difference, microns	Change in Central Subfield Standard Deviation, microns (adjusted for baseline)			
	40	50	60	70
20	172	266	382	518
30	78	120	172	232
40	46	68	98	132

856 Assuming an effective standard deviation of 50 microns and a true difference in mean CST of 30
 857 microns, the required total sample size is 120 eyes to achieve 90% power. Sample size will be
 858 increased to 134 eyes to account for 10% lost to follow-up.

859 **7.4 Outcome Measures Phase 1 (Baseline to completion of the 4-Month/Primary outcome**
 860 **visit)**

861 *Primary Efficacy Endpoint(s)*: Mean change in CST from baseline

862 *Secondary Efficacy Endpoint(s)*:

- 863 • Mean change in retinal volume from baseline

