895 analysis of covariance, with adjustment for baseline CST and randomization stratification factor.
896 Eyes that receive treatment for DME (see section 3.6) will have the last OCT measurement prior
897 to treatment used for the primary analysis. OCTs can be obtained from either Spectralis or Cirrus
898 images. Values from these machines cannot be used interchangeably. OCT values will be
899 converted to a common value for reporting and analyses. The estimated treatment-group
900 difference, 95% confidence interval and 2-sided *P* value will be obtained using robust variance
901 estimation. The assumptions of linearity, normality, and homoscedasticity will be verified using
902 graphical methods. Serious violations may be addressed by transformation of dependent and/or
903 independent variables, non-parametric transformation, categorizing continuous covariates, and/or
904 excluding covariates. Transformation of the dependent variable will be used to obtain valid *p*-
905 values while ensuring statistical model assumptions are met. However, mean treatment group
906 differences, rather than results based on transformed outcomes will be reported for clinical
907 interpretation. Change in CST will be truncated at ± 3 SD to improve robustness of the treatment
908 comparison to CST change outliers.

909 Markov chain Monte Carlo (MCMC) multiple imputation will be used to handle missing data for
910 eyes not treated with an alternative DME treatment. The imputation model will be stratified by
911 treatment group and include the CST measured at randomization visit and change in CST from
912 baseline at all monthly interim visits up to the primary outcome visit along with the randomization
913 stratification factor of recent or planned intravitreous treatment in the non-study eye. MCMC
914 imputation will be used to estimate treatment group differences, 95% confidence intervals, and *P*
915 values; observed data will be used to estimate within treatment group changes.

916 A sensitivity analysis including observed data from participants completing the primary outcome
917 visit (no imputation of missing data) also will be conducted (i.e., complete-case analysis). In
918 addition, a sensitivity analysis including observed data from participants completing the primary
919 outcome visit within -4 weeks and +8 weeks of the target date will be conducted. Status of
920 intravitreous treatment in the non-study eye (recent or planned versus none) will be included as a

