19 Study eyes will be assigned randomly to the two treatment groups in a 1:1 ratio stratified by site
20 and recent (within 4 months) or planned intravitreous treatment in the non-study eye, including
21 intravitreous anti-VEGF and steroid. Participants may have only one study eye enrolled in the
22 randomized trial.

23 **2.0 Efficacy Analysis Plan**

24 **2.1 Primary Outcome Analysis**

25 The primary analysis will consist of a treatment group comparison of mean change in CST from
26 baseline to the primary outcome visit using analysis of covariance, with adjustment for baseline
27 CST and the randomization stratification factor of recent or planned intravitreous treatment in
28 the non-study eye. Given that OCTs can be obtained from either Spectralis or Cirrus images, and
29 that values from these machines cannot be used interchangeably, OCT values will be converted
30 to a common value for reporting and analyses.

31 The primary analysis is an intention-to-treat analysis. All randomized eyes will be included in
32 the primary analysis irrespective of treatment received and will be analyzed according to
33 treatment group assignment at randomization.

34 For the primary analysis, study participants who complete the primary outcome visit without
35 missing data at the primary outcome visit will be considered as the **completer cohort**. Markov
36 chain Monte Carlo (MCMC) multiple imputation with 100 imputations will be used to handle
37 missing data for participants who do not complete the primary outcome visit, i.e., **non-**
38 **completer cohort**. The imputation model will be stratified by treatment group and will include

39 the CST measured at baseline and at all monthly interim visits up to the primary outcome visit
40 along with the randomization stratification factor of recent or planned intravitreous treatment in
41 the non-study eye.

42 For eyes that receive alternative treatment for DME (detailed in Protocol Section 3.6) in Phase 1,
43 data measured after the initiation of the alternative treatment will be considered to be missing
44 before entering the multiple imputation (MI) process, regardless of whether the treatment
45 initiation is per-protocol, and whether the participant completes the primary outcome visit. Then
46 after multiple imputation, the last OCT measurement prior to the initial alternative treatment
47 (LOCF data) will overwrite the MCMC imputed values for all post-treatment visits and will be

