357 In addition, the following will be tabulated by treatment group:

- 358 • For each MedDRA System Organ Class, percentage of participants with at least one
359 serious event
- 360 • Number of adverse events thought by investigator to be related to treatment

361 No formal statistical comparisons will be performed for reported adverse events.

362 **6.0 Additional Tabulations and Analyses**

363 The following will be tabulated according to treatment group:

- 364 • Baseline demographic and clinical characteristics
 - 365 ○ for overall cohort
 - 366 ○ for Phase 2 participants
- 367 • Visit completion rate for each visit (excluding death)
- 368 • Protocol deviations
- 369 • Number of reported device issues
- 370 • Treatment completion

371 In addition, to evaluate the potential contralateral effect, visual acuity, OCT measurements, and
372 treatment for DME in non-study eyes will be tabulated at primary outcome visit by the treatment
373 group assigned to the study eye. These outcomes will be analyzed and presented similarly to the

374 primary and secondary analyses as specified above for the study eyes, with the exception that no
375 imputation will be performed for missing data. If the study eye receives a treatment for DR or
376 DME, the last non-study eye measurement prior to the study eye treatment will be used for
377 analysis.

378 This pilot study is being conducted to determine whether the conduct of a pivotal trial has merit
379 based on an anatomic outcome and to provide information on outcome measures needed to
380 design a pivotal trial. If the results of this study support proceeding with a pivotal trial after
381 evaluation of all the data and discussion within DRCR, information from this study will
382 contribute to designing the pivotal trial. The standard deviation of the difference in visual acuity
383 will be used in the sample size calculation of the pivotal trial. Patient compliance (for example,
384 the proportion of enrolled participants that are randomized and the proportion of randomized
385 participants who comply with the use of the study device post-randomization) will also aid in the
386 design of the pivotal trial.

387 **7.0 OCT Angiography Ancillary Study**

388 At a subset of sites with OCT angiography capabilities, images will be taken at baseline and
389 primary outcome to explore whether there are changes in any features evident on OCT

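### The rule that sets aside study-eye CST after other treatment is triggered only by treatment for DME, so the same treatment given for diabetic retinopathy is left in the primary analysis

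*SAP*

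**What the plan says.** - **SAP 2.1** starts the rule with "For eyes that receive alternative treatment for DME (detailed in Protocol Section 3.6) in Phase 1". Data after that treatment are made missing before imputation, and the last earlier OCT value then replaces the imputed ones. This applies whether or not the treatment met the protocol criteria. The primary dataset takes observed CST from completers who had no alternative DME treatment.
- **Protocol 7.6** agrees: "Eyes that receive treatment for DME (see section 3.6) will have the last OCT measurement prior" to treatment used. Protocol 7.8 and SAP 2.2 carry the rule to the secondary outcomes. The per-protocol cohort (Protocol 7.5, SAP 2.1.2) and SAP Table 1 use the same DME trigger.
- **Protocol 3.6**, which the SAP cites for the definition, is limited to central-involved DME: "Treatment for CI-DME must not be given unless one of the following criteria have been met or" chair approval is given. Protocol 6.1 restricts only alternative treatment for DME.
- **Protocol 2.2.2** treats DR as a separate reason for treatment. Exclusion j reads "Anticipated need to treat DME or DR during the study period (Note: any DME treatment", but its note sends only DME treatment to section 3.6.
- **SAP 6.0**, on the contralateral effect, has a wider rule. Its sentence begins "If the study eye receives a treatment for DR or" and goes on to name DME; the last earlier non-study-eye value is then used.

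**The concern.** CST is the primary endpoint, and the plan sets aside CST measured after anti-VEGF, steroid or other treatment when that treatment is for DME. The reason applies equally when the same agent goes into the same eye for retinopathy, yet the text then keeps the later CST as though only the device had acted. SAP 6.0 shows that DR treatment of the study eye was foreseen. It protects a secondary tabulation of the other eye but not the study eye's own primary outcome. If such eyes fall unequally between the arms, the estimated difference moves for a reason unrelated to the device, and no planned sensitivity analysis would show it. The pilot's purpose is to judge on an anatomic outcome whether a pivotal trial has merit.

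**Working it through.** **1. What happens to a completer's CST after study-eye treatment, as written**

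| Analysis | Treated for DME | Treated for DR only |
|---|---|---|
| Primary (SAP 2.1) | carried forward | observed, post-treatment |
| Sensitivity #1, #3, #4 | carried forward | observed |
| Sensitivity #2 | imputed | observed |
| Sensitivity #5 | excluded | observed |
| Per-protocol (if 70% of sessions completed) | excluded | observed |
| Non-study-eye analysis (SAP 6.0) | cut at treatment | cut at treatment |

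The tipping-point analysis shifts only imputed values, so it does not reach these eyes. Truncation at 3 SD gives little protection. At the design SD of 50 the limit lies about 3 × 50 = 150 microns from the mean, at the top of the range of falls assumed below.

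**2. The plan's own sample size.** Inputs from Protocol 7.3.2: "Type I error rate of 5%, 90% power, and a two-sided test of superiority"; "Assuming an effective standard deviation of 50 microns and a true difference in mean CST of 30" microns. A two-sample t-test gives 59.35 per arm, rounded up to 60, so 120 in total. With 10% loss, 120 / 0.90 = 133.3, rounded up to 134, or 67 per arm at 1:1. Both stated figures reproduce, and so do all 12 cells of Protocol Table 1.

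**3. Size of the shift.** The documents give neither a rate of DR treatment nor its effect on CST, so both are assumed. Let k be the excess of DR-treated eyes in one arm and D the fall in CST that the treatment causes. Then:

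shift in group difference = k × D / 67

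For power, take 60 evaluable eyes per arm: SE = 50 × √(2/60) = 9.13 microns. With a true difference of 30 and the excess in sham, power ≈ Φ((30 − shift)/9.13 − 1.96). With no shift this is 0.908.

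| k | D (microns) | Shift (microns) | Share of 30 | Power |
|---|---|---|---|---|
| 1 | 50 | 0.75 | 2.5% | 0.893 |
| 1 | 150 | 2.24 | 7% | 0.860 |
| 2 | 100 | 2.99 | 10% | 0.841 |
| 3 | 150 | 6.72 | 22% | 0.723 |

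An excess in the PBM arm moves the difference the other way, towards an apparent benefit. Equal numbers with equal effects cancel in expectation. With no true effect and a fixed excess of two eyes at 100 microns, the two-sided rejection rate would be 0.062 instead of 0.050. If the device does not influence DR treatment, the excess arises by chance and is equally likely in either arm.

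**The case against.** The strongest reply has four parts.

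- **Few eyes.** Exclusion j removes eyes expected to need DR treatment, f those with another condition that might need intraocular treatment, h those with major eye surgery anticipated, and i those treated for DR in the past year. The 4-month visit targets 16 weeks; 32 weeks is only the outer allowable limit. This stands and keeps the point modest. It does not settle how an eye that is treated should be handled.
- **Ambiguous text.** Every study eye has central-involved DME, and Protocol 3.5.1 lists PRP and vitrectomy among its examples of alternative treatment. A reader could count any such procedure whatever its indication. This stands in part: the examples sit under treatment planned for DME, so the classification is unclear rather than resolved.
- **Intention to treat.** Keeping observed data is a legitimate treatment-policy choice. The SAP admits that carry-forward understates variance and may favour PBM. An eye treated for DR may also still be using its device, since Protocol 3.6 ties stopping to DME treatment. However, the SAP already gives up treatment policy for these agents when given for DME, even outside protocol criteria, and states no reason for the opposite handling in DR.
- **Systemic anti-VEGF.** A reader might infer that it needs its own analysis rule. Protocol exclusion 10 says of systemic anti-VEGF and pro-VEGF drugs: "These drugs should not be used during the study". Use would be a protocol deviation, and deviations are already tabulated by arm.

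**Conclusion.** The gap is real and should be closed, but its expected effect is small. As written, the indication recorded for an injection decides whether the eye's later CST is kept or replaced, and SAP 6.0 is inconsistent with that. Each excess eye in one arm moves the difference by about 0.7 to 2.2 microns. This rests on an assumed fall of 50 to 150 microns per injected eye, 67 eyes per arm and unequal use between the arms.

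Three stronger readings are not supported:

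- **A known direction of bias.** One might argue that PBM slows retinopathy, so more sham eyes would be treated and the effect diluted. Protocol 1.2 speaks of a possible benefit on DME, and the retinopathy evidence is early lesions in animals. Nothing claims less DR treatment within four months.
- **A large bias.** The 22% figure needs three excess eyes in one arm, each falling 150 microns. No CST effect is given for PRP or vitrectomy.
- **A flaw in the endpoint counting eyes given alternative DME treatment.** That descriptive outcome is properly limited to DME.

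**What to change.** In SAP 2.1, Table 1, 2.1.2 and 2.2, and in Protocol 7.5 to 7.8:

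1. For the CST, retinal volume and visual acuity analyses, the per-protocol cohort and Sensitivity Analyses #2 and #5, define the data-handling trigger as intravitreous or peribulbar anti-VEGF or corticosteroid, retinal laser, or vitrectomy in the study eye, given for DR or DME. This matches SAP 6.0 and settles the ambiguity in Protocol 3.5.1 for analysis purposes.
2. Apply the existing impute-then-carry-forward rule from the date of that treatment. The CST-threshold outcome keeps carry-forward without imputation, as SAP 2.2 already specifies.
3. Add one sensitivity analysis that keeps the observed CST of eyes treated for DR only.
4. Report counts of treated study eyes by arm and indication.
5. Leave the descriptive DME-treatment endpoint limited to DME, and systemic anti-VEGF to the deviation tabulation.

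The cost is wording and one extra model run. SAP 6.0 already requires the study-eye treatment data, and the sample size stays at 134. The downside is that a few more eyes are carried forward, with the limits the SAP already acknowledges. No clinical rule changes.
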